The statistical analyses will be performed after follow-up data collection is completed. The statistical software R will be used for data analyses (Team 2010). Significance of results will be reported using two-tailed tests with a significance level of 5%. 95% confidence intervals will be reported for all estimates. The assumption that the data follows a normal distribution will be visually inspected using residual- and qq-plots, and if the data is not found to be normally distributed, log-scaling will be applied.

The primary outcome is the change in CGAS between 18-month follow-up and baseline. A linear mixed model will be used to model the data. Familiarity will be used as random nested factor in the analysis to accommodate for the non-independence that occurs between siblings that are part of the same family. Age, gender and variables with significant baseline differences between the groups will be used as covariates in the analysis. We report the mean difference in change between the VFI group and the TAU group effect and 95% confidence interval for this effect size.

Secondary Analyses:

Planned analyses for secondary outcomes: Change in mean scores on Child Behavior Checklist (CBCL), Teacher Report Form (TRF) and days of absence from school (\geq 15 %). Parent and family related outcome measures: Family Assessment Device (FAD) and Home Observation Measurement of the Environment (HOME).

Planned analyses for exploratory analysis: Change in mean scores on child related outcome measures: Child Affective Lability Scale (CALS), Behavior Rating Inventory of Executive Function (BRIEF) and Emotion Regulation Questionnaire (ERQ). Child Self-report on: self-esteem (This Is me), health-related quality of life (KIDSCREEN) and resiliency (Child and Youth Resilience Measure -CYRM). Parent and Family related outcomes: Parental Stress Scale (PSS) and Personal and Social Performance Scale (PSP).

For more information on secondary and exploratory outcome measures see study protocol (Müller et al. 2019).

Deviations from the intervention protocol will be handled in the sensitivity analysis. Adherences to intervention protocol have been pre-defined and are explained in detail in the study protocol (Müller et al. 2019)

There has not been planned any interim analysis before data collection has been finished at 18-months post intervention.

Missing Data

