In the ITT analysis, assuming normality of the data and that data is "missing at random" (MAR), missing data will be handled through multiple imputations based on maximum likelihood inference of parameters and imputation of missing data from a linear regression model. The analysis will be based on 100 imputations and iterations until convergence. See table 1 for variables that will be included in the imputations.

Table 1: Variables for imputation on missing data. If not otherwise specified data from baseline and follow-up will be included

Child	Parent/family	Teacher	other
Clinician rated interview	Clinician rated interview	Surveys about the child	Group allocation (experimental/control)
CGAS score	PSP, Primary Caregiver, total score	TRF, total score	
KSADS, any diagnoses (binary: yes/no)	HOME, total score	BRIEF, total sore	
		SRS, total score (baseline)	
Cognitive tests	Surveys about the child		
RIST – total score	CBCL, total score		
TOMAL-II total score	BRIEF, total score		
RCFT - total score	SRS, total score (baseline)		
Self-report surveys:	Self-report surveys:		
KIDSCREEN, total score	PSS Primary Caregiver, total score		

Sensitivity Analysis

To validate results, the following sensitivity analyses will be performed after ITT analysis:

- 1. Impact of outliers (analyses without outliers)
- 2. Per protocol (analyses without protocol violations)
- 3. Attendance (analyses on participants with ≥50% attendance of intended personal meetings in treatment groups)
- 4. Adjusting for covariates (analyses without adjustments)
- 5. For outcome of school absenteeism, a different cut-off will be used for analysis.
- 6. CGAS change for one child per family (for families with multiple children in the study mean change from all children in one family will be used)

Results from the sensitivity analyses will only be reported if negative.

- Ellersgaard, D., K. Jessica Plessen, J. Richardt Jepsen, K. Soeborg Spang, N. Hemager, B. Klee Burton, C. Jerlang Christiani, M. Gregersen, A. Sondergaard, M. J. Uddin, G. Poulsen, A. Greve, D. Gantriis, O. Mors, M. Nordentoft, and A. A. Elgaard Thorup. 2018. 'Psychopathology in 7-year-old children with familial high risk of developing schizophrenia spectrum psychosis or bipolar disorder The Danish High Risk and Resilience Study VIA 7, a population-based cohort study', *World Psychiatry*, 17: 210-19.

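### Cheap improvement: the imputation model in Table 1 leaves out age and gender, which are covariates in the primary CGAS model it feeds

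*SAP*

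**What the plan says.** The Missing Data section assumes data missing at random and plans 100 imputations from a linear regression model for the intention-to-treat analysis. The variable list is fixed by reference: "See table 1 for variables that will be included in the imputations". The caption of Table 1 adds: "If not otherwise specified data from baseline and follow-up will be included".

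Table 1 holds 15 measures: CGAS, KSADS, RIST, TOMAL-II, RCFT and KIDSCREEN for the child; PSP, HOME, CBCL, BRIEF, SRS and PSS from the parent or family; TRF, BRIEF and SRS from the teacher. The only other entry is "Group allocation (experimental/control"). Allocation is known for every randomised child, so the table is a list of what goes into the imputation model, not only of what is to be filled in.

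Of the primary model the SAP says: "Age, gender and variables with significant baseline differences between the groups will be used as covariates in the analysis". It also says: "Familiarity will be used as random nested factor in the analysis to accommodate for the non-independence that occurs between siblings". The reported quantity is described as follows: "We report the mean difference in change between the VFI group and the TAU group effect", with its 95% confidence interval.

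Age, gender and family do not appear in Table 1, and nothing else in the SAP adds them to the imputation.

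**The concern.** An imputation model should contain at least the variables of the analysis that will use the imputed values. Here it does not. A child with missing follow-up CGAS gets a value drawn as if age and gender carried no information beyond the listed scores, and the completed data then go into a model that adjusts for age and gender.

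Missing at random is an assumption conditional on the variables in the imputation. If older children in one arm are lost more often than older children in the other, and age is related to CGAS change, the assumption fails given Table 1 but would hold once age is added. The adjusted primary model fitted to complete cases would already protect against that dropout pattern, and imputing without age removes part of the protection. What is at stake is a bias in the primary treatment effect that two variables, normally known for every child, would remove.

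**Working it through.** **1. Terms side by side.** Primary model: CGAS, group, age, gender, family, plus any covariate with a significant baseline difference. Table 1 contains CGAS and group. Age, gender and family are absent. Covariates chosen on baseline differences are covered only if they happen to be listed.

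**2. Inputs.** From the SAP: 37 children per group, a 10-point CGAS change, two-sided 5%. Not in the SAP, so assumed: fraction missing p = 10% or 30%; correlation r of age with CGAS change, 0.1 to 0.3; dropout odds ratio 2 per SD of age, so k = ln 2 = 0.693.

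**3. Approximate formula.** Without age in the imputation, the completed mean of an arm stays at the mean of its observed children. Where dropout depends on age with log odds ratio k, the mean age of the observed children shifts by about k × p SD, and their mean change by about r × k × p SD. Age over all randomised children is balanced, so adjusting for it afterwards does not undo the shift. Hence

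bias ≈ r × p × |k(VFI) − k(TAU)|, in SD of CGAS change.

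- Opposite directions by arm (difference 2 × 0.693 = 1.386): at 10% missing, 0.1 × 0.1 × 1.386 = 0.014 to 0.3 × 0.1 × 1.386 = 0.042. At 30%, 0.1 × 0.3 × 1.386 = 0.042 to 0.3 × 0.3 × 1.386 = 0.125.
- One arm only (difference 0.693): 0.007 to 0.021 at 10%; 0.021 to 0.062 at 30%.
- Equal dependence in both arms: 0.

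**4. Simulation.** With 74 children, r = 0.3 and opposite directions, repeated-trial simulation gives a bias of 0.042 SD at 10% missing and 0.117 SD at 30%, close to the formula. At r = 0.1 it gives 0.01 and 0.04 SD. With age and gender added to the imputation it is 0.005 SD or less. The age- and gender-adjusted model on complete cases, with dropout otherwise random, is biased by 0.003 SD or less.

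**5. In CGAS points.** The SAP states neither the SD nor the power. From n = 2(z₁ + z₂)² SD² / 10², 37 per group is reached with an SD of about 15.3 at 80% power (2 × 2.80² × 15.3² / 100 ≈ 36.7) or about 13.2 at 90% (2 × 3.24² × 13.2² / 100 ≈ 36.6). Taking that SD for the change:
- opposite directions: 0.01 × 13.2 = 0.1 to 0.04 × 15.3 = 0.6 points at 10% missing; 0.04 × 13.2 = 0.5 to 0.12 × 15.3 = 1.8 points at 30%;
- one arm only: 0.1 to 0.3 points at 10% (0.01 × 13.2 to 0.02 × 15.3); 0.3 to 0.9 points at 30% (0.02 × 13.2 to 0.06 × 15.3).

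**6. Gender.** For a balanced binary covariate with correlation 0.2 to 0.3 and a dropout odds ratio of 2.25 between the sexes, opposite by arm, simulation gives 0.01 to 0.02 SD at 10% missing and 0.05 to 0.08 SD at 30%.

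**7. Family.** With a true sibling intraclass correlation of 0.4, the Table 1 imputation yields 0.32 to 0.37 at 10% missing and 0.24 to 0.31 at 30%. With age, gender and a family random intercept it yields 0.37 to 0.40 and 0.35 to 0.40. The reported standard error divided by the true one hardly moves: 0.99 to 1.06 against 0.98 to 1.04 at 10%, and 1.05 to 1.15 against 1.04 to 1.13 at 30%.

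**The case against.** The bias is conditional, and nothing in the SAP suggests that dropout depends on age or gender differently by arm. That stands. It is why the point is an improvement and not an error in the result.

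The assumed correlations can also be called generous. If the ages 6 to 12 have an SD of about 2 years (an assumption), the two ends lie 3 SD apart. A correlation of 0.3 then means that 6- and 12-year-olds differ in expected change by 0.3 × 3 × 13.2 ≈ 12 to 0.3 × 3 × 15.3 ≈ 14 points, more than the 10 points the sample size is built on. A correlation of 0.1 means 4 to 5 points. The upper ends of the ranges should be read in that light. A separate simulation with a slope of 1 point per year and opposite-direction missingness gave a bias of 0.11 to 0.26 points at 10% missing and 0.44 to 0.64 points at 30%.

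The listed scores may partly stand in for age. With three cognitive tests each correlated 0.5 with age (r = 0.3, odds ratio 2, opposite directions), simulated bias falls from 0.040 to 0.017 SD at 10% and from 0.116 to 0.062 SD at 30%. This softens the point but does not remove it.

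The planned sensitivity analyses do not settle it. The unadjusted analysis drops covariates from the model but adds none to the imputation, and the analysis of family means deals with siblings, not with age or gender.

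**Conclusion.** The point holds in a limited form. Table 1 fixes an imputation model without age and gender, and the primary model contains both. If age or gender predicts CGAS change and dropout depends on it differently by arm, the adjusted effect is biased. Under the assumptions above the bias is about 0.01 to 0.02 SD (one arm) or 0.01 to 0.04 SD (opposite directions) at 10% missing, and 0.02 to 0.06 or 0.04 to 0.12 SD at 30%. Without differential dropout it is about zero.

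Two stronger readings are tempting, and the document supports neither.

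- **Family.** A reader might infer that leaving family out makes the CGAS interval too narrow. It dilutes the sibling correlation, but the estimate and its interval do not change materially, and the SAP reports those, not the correlation.
- **Secondary outcomes.** A reader might infer that two secondary outcomes are wrongly left unimputed, since the SAP names "Teacher Report Form (TRF) and days of absence from school" and "Parent and family related outcome measures: Family Assessment Device (FAD) and Home Observation Measurement of the Environment (HOME"), while Table 1 lacks FAD and absence. But the Missing Data section ties imputation to the intention-to-treat analysis, which the SAP heads as the primary analysis. Table 1 also includes measures that are not among the listed outcomes (RIST, TOMAL-II, RCFT, SRS) and omits four of the eight exploratory outcomes (CALS, ERQ, This Is Me, CYRM). It reads as a set of auxiliary predictors for CGAS, so these absences are not a shown defect.

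**What to change.** Add age, gender and any covariate selected for the primary model to the variables used to impute CGAS. This is a line in Table 1 and two or more terms in the R call; sample size, alpha and endpoint stay as they are.

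The cost is a longer predictor list. Table 1 already gives 15 baseline scores, 13 follow-up scores (the two SRS entries are baseline only) and group: 15 + 13 + 1 = 29 variables, so up to 28 predictors of follow-up CGAS for about 2 × 37 = 74 children. Age and gender make that up to 30.

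Optionally, account for family in the imputation, by a family random intercept or a simpler family-level term if few families have siblings in the trial. This preserves the sibling correlation but will not narrow the CGAS interval. With few sibling families the family variance is weakly estimated: at a true correlation of 0.2 and 30% missing, two-level imputation gave 0.26 to 0.32, against 0.22 to 0.27 in full data.

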Statistical Analysis Plan (SAP) for: VIA Family—a family-based early intervention versus treatment as usual for familial high-risk children.

ClinicalTrials.gov, NCT03497663,

SAP version 1. 25.05.2021

Roles and responsibility

[name] (ADM)

[name] (IG)

[name] (NT)

[name] (NH)

[name] (MN)

[name] (AT)

AT is primary investigator, ADM and NT wrote the SAP.

Background

Children of parents with mental illness (COPMI) have an increased lifetime risk for developing a mental illness themselves (Rasic et al. 2014). Already during childhood COPMI have an increased risk for experiencing pediatric psychopathology and they have lower levels of functioning in their everyday life compared to children without parental mental illness (Ellersgaard et al. 2018). Children who are born to and grow up with parents who experience a severe mental illness (SMI) have a twofold risk: an enhanced genetic and a psychosocial risk.

There is a need for early interventions and preventive strategies in order to help children with current their problems while also enhancing resilience in the families and thus, hopefully prevent the development of mental illness in the children later in life.

Objectives and Trial design:

The VIA Family study aims to investigate the effect of an early intervention for families with parental SMI on children's level of functioning and psychological wellbeing.

The trial is a randomized controlled trial in a two-armed parallel group design. The study aims to test for superiority of the VIA Family Intervention (VFI) compared to treatment as usual (TAU).

The participating families were randomly assigned to VFI or TAU. The allocation ratio was 1:1. Randomization was stratified by parental inclusion diagnosis. Randomization was performed through the randomization module within the electronic database REDCap (Harris et al. 2009).

For more information see study protocol (Müller et al. 2019)

Sample size

The power calculation of the sample size on the primary outcome of the study, the Children's Global Assessment Scale (CGAS), detected that the study needed to include 37 children in each group to show a high effect size of a change of 10 points on the CGAS, a scale from 1-100. For further details on sample size calculation see study protocol (Müller et al. 2019).

Trial population

All participants were screened for eligibility criteria before randomization.

[figure not shown]

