Eligibility criteria were: Having (at least) one child between age 6-12. Living in the municipalities of Frederiksberg or Copenhagen (Denmark). The parent has been registered in the Danish registers as having been diagnosed with one of the following psychiatric diagnoses: Schizophrenia Spectrum Disorder, Bipolar Disorder, Recurrent severe or moderate depression, within child's life. Comorbid disorders were allowed.

Exclusion criteria were: Parent with insufficient Danish language skills to be able to engage in treatment. Having received intensive family treatment in primary sector within the last 26 weeks before study participation.

For more detailed information see study protocol (Müller et al. 2019).

See CONSORT flow-diagram for screening, inclusion process and follow-up (Fig. 1)

Fig. 1 CONSORT 2010 Flow Diagram

Withdrawal/Follow-up

Baseline characteristics of the study population will be presented in a descriptive table, presenting any possible differences between the two groups and the level of statistical significance.

Withdrawal from the study will be registered and reason for lost to follow up will be registered if possible. All participants who are missing at random will be included in the ITT analyses, see CONSORT diagram for drop out.

Statistical Analyses

Primary outcome

The primary outcome of the study is the change in CGAS. More precisely, the analysis will compare mean changes between baseline and 18 months in the CGAS to the VFI group.

The CGAS is a clinician rated scale from 1-100 (the higher the better) indicating the worst level of child's functioning within the last month. The CGAS will be used as a continuous outcome measure in the analysis.

The research question for the primary outcome is: Do children in the VFI group increase significantly more in CGAS at postintervention, when compared to the TAU group?

Primary Analysis: Intention-To-Treat

The primary analysis will be performed based on intention-to-treat (ITT) principles, meaning that the ITT population includes all randomized participants irrespective of their dropout status.

All outcome data will be analyzed collectively after the last participant has finished post intervention assessment. We will conduct an analysis of the primary outcome of the study followed by sensitivity analysis for the primary outcome. Further secondary analysis will be performed. See study protocol for an elaboration of primary and secondary outcomes (Müller et al, 2019).

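### The attendance sensitivity analysis selects on post-randomisation behaviour, does not say how TAU families are handled, and cannot validate the ITT result

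*SAP*

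**What the plan says.** The SAP describes a two-arm parallel superiority trial of VFI against TAU (Objectives and Trial design). Under Primary Analysis: Intention-To-Treat, "the ITT population includes all randomized participants irrespective of their dropout status". Under Secondary Analyses, "Deviations from the intervention protocol will be handled in the sensitivity analysis", and the definition of adherence is left to the protocol.

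The Sensitivity Analysis section opens: "To validate results, the following sensitivity analyses will be performed after ITT analysis". Its third item is "analyses on participants with ≥50% attendance of intended personal meetings in treatment groups". The section closes: "Results from the sensitivity analyses will only be reported if negative".

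The SAP does not say which TAU children enter item 3 or what would count as an intended meeting in TAU. It gives no method to deal with selection on attendance and attaches no caveat to the result.

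**The concern.** Randomisation makes the arms comparable as randomised. It does not make the VFI families who attended comparable with TAU as a whole. Attendance is a choice made after allocation, and it may go with things that also drive change in CGAS, such as family resources, motivation or the severity of current problems. Once low attenders are removed from one arm, the difference between arms mixes any intervention effect with the difference between attenders and non-attenders.

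What is at stake is the use made of the result. An analysis with this bias is offered as a check on ITT, so agreement between the two would be taken as support. The reporting rule adds to this. If negative means unsupportive of the ITT finding, a spuriously favourable attender result goes unreported, and readers may take the silence as a check passed. A spuriously unfavourable one would be reported and could count wrongly against the intervention.

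**Working it through.** **Inputs from the SAP.** 37 children per group and a 10-point CGAS difference (Sample size); 1:1 allocation; two-sided 5% tests; retention at 50% attendance or more.

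**Inputs assumed, because the SAP gives none.** SD of CGAS change, share p of VFI children retained, and correlation r between attendance propensity and CGAS change.

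**Step 1: is SD 15 reasonable?** The SAP gives neither SD nor power, so 37 cannot be reproduced from its own inputs. At 80% power, n = 2 × (1.96 + 0.8416)² × (15/10)² = 35.3, or 36 per group by the normal approximation and 37 by the t-test. An SD of 13 at 90% power gives the same pair, 36 and 37. SD 15 therefore fits the stated size but is not the only value that does.

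**Step 2: bias under no effect, VFI filtered and all TAU kept.** With attendance propensity and CGAS change bivariate normal, bias = r × SD × φ(z)/p, where z is the cut-off that leaves a share p above it.

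| p | φ(z)/p | r = 0.2 | r = 0.3 | r = 0.4 |
|---|---|---|---|---|
| 0.8 | 0.280/0.8 = 0.350 | 1.05 | 1.57 | 2.10 |
| 0.7 | 0.348/0.7 = 0.497 | 1.49 | 2.24 | 2.98 |
| 0.6 | 0.386/0.6 = 0.644 | 1.93 | 2.90 | 3.86 |

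The range is 1.05 to 3.86 points, or about 10% to 40% of the 10-point target. At r = 0 the bias is zero. Changing the sign of r changes the sign of the bias: at r = -0.3 it is -2.2 points for p = 0.7. The bias scales with SD, so at 13.27 (the SD implied by 37 per group at 90% power) each entry is multiplied by 13.27/15 = 0.885.

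**Step 3: effect on the test.** In simulation with 37 per arm, no true effect and siblings ignored, false significant results favouring VFI are nominally 2.5%. At r = 0.3 they rise to 6.2% (p = 0.8), 8.0% (p = 0.7) and 10.4% (p = 0.6). Over r = 0.2 to 0.4 the two-sided 5% test rejects about 6% to 15% of the time.

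**Step 4: the other readings of item 3.**
- Both arms filtered to the same share with the same attendance-outcome link: bias about 0.
- Both arms filtered to the same share (70% or 50%), r = 0.3 in VFI but 0 in TAU: 2.2 or 3.6 points.
- r = 0.3 in both arms, but TAU filtered more loosely (90% kept against 70% or 50% in VFI): 1.4 or 2.7 points.
- TAU left out: there is no between-arm contrast, so nothing about the ITT effect is checked.

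**Step 5: the alternative.** If TAU has no access to the intervention, the complier-average estimate is the ITT difference divided by p. Its interval is therefore wider by about 1/p: 1/0.8 = 1.25 to 1/0.6 = 1.67. The standard error of the ITT difference is 15 × √(2/37) = 3.49, giving 4.4 to 5.8 after division. Simulation under no effect gave means of -0.26 to 0.02 and SDs of 4.4 to 6.0, in line with this.

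**The case against.** A reader might infer that the SAP compares high-attending VFI families with all control families. It does not say so: the wording refers to treatment groups in the plural and fixes no comparator. The SAP also does not describe TAU, so it cannot be asserted from this document that attendance has no counterpart there. This part of the objection stands. It does not rescue item 3, because only identical filtering with an identical attendance-outcome link removes the bias, and nothing in the SAP supports that.

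A reader might also infer that the bias must favour VFI. The documents do not support that. The outcome is change in CGAS, not level. Better-functioning children have less room to improve, and families in greater difficulty may attend more, so the correlation could be zero or negative.

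A third tempting reading is a published neutral ITT result beside a positive attender result. The reporting rule works against that, since a favourable sensitivity result would not be reported. What remains is the risk that silence is taken as confirmation.

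Finally, item 3 is one of six analyses that follow ITT and cannot change it. That stands and limits the weight of the point. It is also fair that a complier-average estimate is close to a rescaled ITT estimate and so adds little independent confirmation. Its binary form is inflated if families below 50% attendance also benefit.

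**Conclusion.** The concern holds in a limited form. Item 3 selects on behaviour after randomisation, leaves the handling of TAU open, and is presented as validating ITT, which it cannot do. On the likely reading (VFI filtered, all TAU kept), the bias under no effect is about 1.1 to 3.9 points in absolute size for correlations of 0.2 to 0.4 in absolute value. It is upward if the correlation is positive, downward if negative, and absent at zero. These figures rest on an assumed SD of 15, 60% to 80% retention, normality and no allowance for siblings; none of these values comes from the SAP. The primary ITT inference is untouched. The item should be corrected, but it does not threaten the trial's main conclusion.

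**What to change.** Replace item 3 with a complier-average causal effect of attending at least 50% of intended meetings. Use randomised arm as the instrument (two-stage least squares), the same covariates as the primary model, standard errors clustered by family, and every randomised child. Add a version with percent attendance as a continuous dose, because families below 50% may also gain.

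The SAP should state the exclusion restriction, how any TAU access to the intervention is measured and handled, and that the estimate answers the attendance question and is not independent validation of ITT.

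If a filtered comparison is kept, say which TAU children enter it, label it descriptive and non-randomised, and report it whatever its result.

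The cost is some SAP wording and a few lines of R. The price in precision is an interval about 1.25 to 1.7 times as wide as that for ITT, together with an assumption that the data cannot fully test.

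### The SAP makes reporting of its six planned sensitivity analyses depend on their results, through the undefined word 'negative'

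*SAP*

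**What the plan says.** The SAP section Sensitivity Analysis opens with a commitment: "To validate results, the following sensitivity analyses will be performed after ITT analysis". Six numbered items follow:

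1. analysis without outliers;
2. per protocol;
3. participants with at least 50% attendance;
4. analysis without covariate adjustment;
5. another cut-off for school absenteeism;
6. one CGAS change value per family.

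The section ends with the reporting rule: "Results from the sensitivity analyses will only be reported if negative".

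Other parts of the SAP rely on these checks:

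- The section Primary Analysis: Intention-To-Treat says the primary analysis will be "followed by sensitivity analysis for the primary outcome".
- The section Secondary Analyses says: "Deviations from the intervention protocol will be handled in the sensitivity analysis".
- On the primary model, the SAP says: "Age, gender and variables with significant baseline differences between the groups will be used as covariates in the analysis". Item 4 is the check on that choice.
- The same part of the SAP models family as a random factor because siblings are not independent. Item 6 is the check on that.

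**The concern.** A sensitivity analysis informs the reader by showing how far the estimate and its interval move when one choice in the main analysis is changed. A rule that publishes it only for certain results removes that information selectively. Here the rule also turns on a word with no definition, so the reading could be chosen once the results are known.

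What is at stake is the reader's ability to judge whether the CGAS result is robust to protocol deviations, poor attendance, data-driven covariate selection and clustering within families. The main estimate itself is not at stake.

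**Working it through.** No arithmetic applies. The check is a reading of the SAP against itself.

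**Step 1: count.** Six analyses are listed, and the reporting sentence makes no exception, so all six fall under it. Item 6 names CGAS, the primary outcome. Item 5 names school absenteeism, a secondary outcome. Items 1 to 4 name no outcome. The ITT section ties sensitivity analysis to the primary outcome, but it does not say that items 1 to 4 exclude secondary outcomes.

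**Step 2: look for a definition.** No section of the SAP says what 'negative' means. Three readings are possible: (a) non-significant, (b) estimate favouring TAU, (c) discordant with the ITT result.

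**Step 3: apply each reading.**

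| Primary result | Sensitivity result | (a) Non-significant | (b) Favours TAU | (c) Discordant |
|---|---|---|---|---|
| Significant for VFI | Significant for VFI | withheld | withheld | depends on criterion: withheld if judged on direction and significance, open if size counts |
| Significant for VFI | Non-significant, still leaning to VFI | reported | withheld | depends on criterion: reported if significance counts |
| Null | Significant for VFI | withheld | withheld | reported if significance counts |
| Null | Null | reported | depends on sign | withheld if judged on significance |

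The same pair of results can be published or withheld according to the reading. Under (c) the outcome also depends on a criterion for discordance that the SAP does not give.

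**Step 4: which reading fits best.** The stated purpose is to validate the main result, which points to (c): report a check when it fails to confirm. On that reading the failures are disclosed. What is lost is every supportive check, with its estimate and interval.

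**Step 5: what the rule covers.** Items 2 and 3 carry the SAP's stated handling of deviations from the intervention protocol. Item 4 tests the effect of adjusting for covariates chosen partly because they differ significantly at baseline. Item 6 tests the family random factor. Whether the reader sees any of these depends on the result.

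**Step 6: two loosely described items.** Item 1 gives no rule for what counts as an outlier. Item 5 says only: "For outcome of school absenteeism, a different cut-off will be used for analysis". The section Secondary Analyses gives 15% as the main cut-off, but the alternative is not stated in this SAP.

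**The case against.** The strongest defence is that 'negative' plainly means 'does not confirm'. Bad news is then always disclosed and silence signals agreement. Since the SAP also commits to performing all six, silence should mean performed and concordant. Much of this stands: it is the best-fitting reading, and under it the rule does not tilt towards VFI. It does not rescue the rule, because no threshold for agreement is set, a reader cannot verify that an unreported check was done, and the movement of the estimate stays hidden.

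A reader might infer several stronger points that the SAP does not support:

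- *That the rule is biased in favour of VFI.* This is not so on the best-fitting reading. On readings (a) and (b), after a null primary result, the rule would withhold a check that favours VFI.
- *That a large fall in the estimate would go unreported however 'negative' is read.* Under reading (c) this requires discordance to be judged on direction and significance alone, a criterion the SAP does not state. The fall cannot be sized in CGAS points either: the SAP gives 37 children per group and a 10-point difference, but no standard deviation or power.
- *That readers could never learn the outlier rule or the alternative cut-off.* The sentence restricts results; it does not stop a methods section from stating them. All that can be said is that they are not stated in this SAP. The protocol, to which the SAP refers, is not at hand.
- *That the rule contradicts "95% confidence intervals will be reported for all estimates".* That sentence stands beside the test and significance level and reads naturally as a format rule for whatever is reported. The point does not depend on it.

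**Conclusion.** The point holds as a reporting defect and should be fixed. The SAP states the rule explicitly, so this is not a detail left to the protocol. Its extent is six of six planned sensitivity analyses, with no definition of the word that decides whether each is published.

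The primary estimate and its confidence interval are unaffected, and no numerical bias is claimed. The harm is lost transparency: on the charitable reading, supportive checks and the movement of the estimate are hidden; on the other two, a check significantly favouring VFI after a null primary result is hidden as well. The conclusion rests only on the SAP's wording and needs no assumption about power, variance or the observed effect.

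**What to change.** Replace the closing sentence of the section Sensitivity Analysis with:

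> Estimates and 95% CIs from all pre-specified sensitivity analyses will be reported beside the corresponding main result, whatever their direction or significance.

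A supplementary table is enough. It should state the outlier rule used for item 1 and the alternative absenteeism cut-off used for item 5, and both are better fixed in the SAP before analysis. With everything reported, 'negative' no longer needs a definition.

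The cost is one sentence and one table. No new data or analyses are required, since all six are already planned.
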